1.2 Previous Nonclinical Research and Clinical Trial Experience in Tc 99m Tilmanocept

A detailed evaluation of the nonclinical evaluations from subcutaneous (SC) and IV routes of administration, clinical pharmacokinetics (PK), clinical efficacy, and clinical safety of Tc 99m tilmanocept can be found in the accompanying Investigator's Brochure supplied by Navidea Biopharmaceuticals, Inc.

1.2.1 Nonclinical Evaluations – Subcutaneous Administration

Nonclinical studies of Tc 99m tilmanocept demonstrated that the drug selectively binds to its intended receptor (the CD206 mannose binding receptor), and is well tolerated by rats, rabbits, guinea pigs, and dogs.

PK data obtained from nonclinical studies demonstrated rapid absorption into the plasma. Urinary excretion was a major pathway of elimination. Tc 99m tilmanocept exhibited rapid clearance from the injection site, rapid uptake by the local lymph node, and low uptake by the remaining lymph nodes. Tilmanocept was well tolerated at all doses tested in nonclinical safety pharmacology studies and in single and repeated dose toxicology studies in rats, rabbits, and dogs. In some studies in rabbits and dogs, tilmanocept acted as a local irritant of the subcutis or skeletal muscle, and induced mild inflammation and tissue degeneration. The no-observed adverse-effect level (NOAEL) was $42\mu g/kg/day$. Tilmanocept was not mutagenic or genotoxic in vitro or in vivo. No signs or symptoms of hypersensitivity were observed in a study in guinea pigs.

1.2.2 Nonclinical Evaluations – IV Administration

In preparation to initiate the IV route of administration, 11 preclinical tests were conducted to assess safety, toxicity, and interaction potential at doses hundreds to thousands of times the expected maximum human dose, as summarized in Table 1. The nonclinical evaluations yielded safety and pharmacokinetics profiles that were appropriate for initiation of IV dosing in clinical trials. Nonclinical study results can be found in the accompanying Investigator's Brochure.

Type of Study / Description	Test System	Method of Administration	Dosing
Central nervous system safety pharmacology	Rat	Intravenous	37, 190, and 380 μg/animal or equivalent 490X and 61X the anticipated study doses of 50 μg and 400 μg in humans
Expanded single-dose toxicology (including toxicokinetics and local tolerance)	Rat	Intravenous	37, 190, and 380 μg/animal or equivalent 490X and 61X the anticipated study doses of 50 μg and 400 μg in humans
Respiratory Safety Pharmacology Evaluation Using Head- Out Plethysmography of Tilmanocept following Intravenous Bolus Injection in Male Rats	Rat	Intravenous	60, 120, and 300 μg/animal or equivalent 320X and 41X the anticipated study doses of 50 μg and 400 μg in humans
In Vitro Evaluation of Tilmanocept as an Inhibitor of Cytochrome P450 (CYP) Enzymes in Human Liver Microsomes	Human Liver Samples	In vitro	0.6 to 600 nM
In Vitro Evaluation of Tilmanocept as an Inhibitor of Human ABC and SLC Transporters	Human Liver Samples	In vitro	0.04, 0.4 µM
Pharmacokinetics, Excretion, and Distribution by Quantitative Whole- Body Autoradiography Following Intravenous Administration of 99mTc-Tilmanocept in Rats	Rat	Intravenous	25 μg in 0.5 mL with collection of blood, urine, feces, and carcasses for QWBA
Hemolysis and protein flocculation	Human blood samples	In vitro	2.5, 25, and 250 μg/mL whole human blood
Target profiling screen (K, Na, and Ca ion channels)	Ion Channel	In vitro	0.025 to 0.5 mg/mL

Table 1Preclinical Tests

1.2.3 Clinical Pharmacokinetics (IV)

Clinical PK was evaluated in IV administered Tc 99m tilmanocept in the Phase 1 and 2 trial NAV3-21 (NCT02865434). In this trial, 12 subjects (6 RA/6 HC) were administered the maximum dose of 400 mcg tilmanocept radiolabeled with 10 mCi of Tc 99m and urine and blood data were non-compartmentally modeled to assess potential differences in drug distribution and elimination by disease group (active RA vs. HC).

Subject-level whole blood PK parameters were assessed between HC subjects (n = 6) and subjects with active RA (n = 6) to evaluate potential differences between mean maximum concentration (C_{max}), mean area under the concentration-time curve (AUC_{0-t}), mean area under the concentration-time curve extrapolated to infinity (AUC_{0- ∞}), mean clearance, mean half-life (t_{1/2}), or mean elimination rate constant (λ_z) across each disease group (Table 2). The geometric mean of whole blood clearance was 26.5 mL/min for HC subjects and 24.8 mL/min for RA patients.

Group	Statistic	Clearance	AUC(0-t)	AUC(0-∞)	Cmax	T1/2
		(mL/min)	(min*nCi)	(min*nCi)	(nCi)	(min)
	n	6	6	6	6	6
	Mean	27.3	235258.0	370580.1	1244.2	759.0
	Std Dev	7.36	50010.28	92535.92	500.36	134.20
	CV%	26.9	21.3	25.0	40.2	17.7
HC	Geometric Mean	26.5	230853.1	360357.6	1155.5	749.3
	Lower 90% Cl	21.26	193698.75	290005.04	809.55	648.36
	Upper 90% Cl	33.04	275134.27	447777.17	1649.33	865.85
	n	6	6	6	6	6
	Mean	25.5	268110.7	396026.4	2043.8	719.1
	Std Dev	6.18	61667.51	101351.07	1211.86	138.10
	CV%	24.3	23.0	25.6	59.3	19.2
RA	Geometric Mean	24.8	262309.5	385984.3	1761.9	707.4
	Lower 90% Cl	20.11	217187.41	315475.79	1078.28	598.97
	Upper 90% CI	30.59	316806.03	472251.44	2878.94	835.46

Table 2Whole Blood PK Parameter Summaries by Group

Similarly, subject-level urinary PK parameters including maximum rate, AUC_{0-t} , or percent recovered were assessed for HC subjects (n=6) and subjects with active RA (n=6) to evaluate potential differences between disease groups (Table 3). The geometric mean of urine percent recovered was 7.4% in HC subjects and 6.7% in RA patients.

Group	Statistic	Percent Recovered ^a	AUC(0-t) (h*nCi)	Max Rate (nCi/h) ^b
	n	6	6	6
	Mean	7.6	1468788.9	949280.7
	Std Dev	2.07	432723.27	236916.28
HC	CV%	27.2	29.5	25.0
	Geometric Mean	7.4	1411786.8	924858.6
	Lower 90% CI	5.84	1088888.09	752742.08
	Upper 90% CI	9.28	1830437.75	1136329.94
	n	6	6	6
	Mean	6.9	1384642.0	841331.0
	Std Dev	1.74	313600.65	227308.94
RA	CV%	25.2	22.6	27.0
	Geometric Mean	6.7	1355137.9	817282.6
	Lower 90% CI	5.46	1123310.11	659111.71
	Upper 90% CI	8.33	1634810.07	1013410.74

Table 3Urine PK Parameter Summaries by Group

^a Percent recovered is the cumulative amount of radioactivity divided by the dose and multiplied by 100.

^b Maximum observed excretion rate, calculated as (radioactivity*volume)/ (end time – start time).

A comparison of the PK parameters in subjects with active RA and HC subjects does not reveal any apparent differences in the elimination of radioactivity from the body.

1.2.4 Clinical Efficacy

1.2.4.1 NAV3-23 (SC)

This was an open-label, multicenter study of Tc 99m tilmanocept by subcutaneous injection in patients with active RA and healthy controls. Tilmanocept was administered SC at 1 of 2 mass doses: [1] 50 mcg (Cohorts 1 & 3), or [2] 200 mcg (Cohorts 2 & 4). Both mass doses were radiolabeled with 2 mCi of Tc 99m. A total of 18 subjects were enrolled and evaluated (9 active RA, 9 HC). Imaging was performed 60 ± 15 minutes post injection. The following performance conclusions were drawn upon study completion:

- Based on data from this study and parallel pathology studies, Tc 99m tilmanocept localizes to activated macrophage-infiltrated joints at doses of 50 µg and 200 µg radiolabeled with 2.0 mCi (74.0 MBq) by SC administration.
- Across all combined RA subjects, swollen/tender joints demonstrating the highest proportions of localization include the wrists and knees.
- Based on qualitative image evaluation, Tc 99m tilmanocept does not show differences in localization between 2 to 3 and 4 to 6-hour planar imaging within dosing groups.
- Tc 99m tilmanocept demonstrates a greater frequency of localization to swollen/tender joints at 200 mcg/2.0 mCi than 50 mcg/2.0 mCi.
- There is an overall lack of concordance between qualitative observation of Tc 99m tilmanocept localization to swollen/tender joints identified in DAS28 joint count

assessment. Swollen/tender joints did not appear to be reliable predictors of presumed abnormal activated macrophage infiltration and overall disease progression when used as an isolated diagnostic system.

- Increased tilmanocept mass dosing, increased Tc 99m specific activity, and other routes of administration may enhance localization and anatomic delineation in tilmanocept-positive joints of RA patients.
- The potential for using Tc 99m tilmanocept to delineate macrophage infiltration in RAaffected joints may allow for earlier RA-specific treatment beyond the current standard of care ACR/EULAR criteria.

1.2.4.2 NAV3-21 (IV)

This was an open-label, multicenter, dose-escalation safety with PK and dosimetry study of Tc 99m tilmanocept by IV injection in HCs and subjects with active RA. Thirty-nine subjects were enrolled. A total of 27 subjects with active RA were enrolled to Groups 1 to 9 in the dose escalation phase. Group 10 consisted of 6 HCs (3 female and 3 male) and Group 11 consisted of 6 subjects with active RA (3 female and 3 male). Tilmanocept was administered IV at 1 of 3 mass doses: 50 mcg, 200 mcg, or 400 mcg. Within each mass dose group, tilmanocept was radiolabeled with 1 of 3 Tc 99m doses: 1 mCi, 5 mCi, or 10 mCi. Subjects in Groups 10 and 11 received the maximum dose of 400 mcg/10 mCi. Imaging was performed 60 ± 15 minutes p.i. The following clinical efficacy conclusions were drawn upon study completion:

- The TUV_{brain(average)} readout provides an objective means of quantification of Tc 99m tilmanocept localization when administered at the calculated optimal dose of 150 mcg/10 mCi and planar images are acquired 60 to 180 minutes after drug administration.
- Joint-specific localization of activity and joint-specific clinical symptomology were not fully concordant. Within the spectrum of RA disease involvement, there may be a decoupling of the causal active immune process and subsequent clinical sequelae. We surmise that imaging and quantification of Tc 99m tilmanocept uptake may provide a fuller and more accurate, responsive, and objective measure of RA disease activity than can be obtained from clinical assessments alone. Future studies will examine whether the approach to image acquisition and calculation of TUV can be further refined.

1.2.4.3 NAV3-31 (IV)

This is an ongoing open-label, multi-center, single and repeat-dose study designed to evaluate the reliability and sensitivity of TUV assessments in HCs and subjects with active RA. One-hundred and five evaluable subjects will be enrolled. Tilmanocept is administered IV at a dose of 150 mcg tilmanocept radiolabeled with 10 mCi Tc 99m. Clinical efficacy conclusions for this study are still in progress.

1.2.5 Clinical Safety

1.2.5.1 NAV3-23 (SC)

The NAV3-23 (NCT02683421) safety evaluation included all trial subjects injected with Tc 99m tilmanocept (N = 18). The AE monitoring was performed from the time of dose administration until completion of onsite safety assessment. There was 1 AE that was possibly related to and 1 AE that was probably related to Tc 99m tilmanocept. However, there were no AEs that led to trial discontinuation, and no SAEs were observed. There were no deaths on trial.

1.2.5.2 NAV3-21 (IV)

The primary safety endpoint of the NAV3-21 study was evaluated by examining the incidence of AEs, changes over time in clinical laboratory tests, physical exams, electrocardiogram (ECG) parameters, and vital signs. The safety evaluation included all subjects who were enrolled in the study and administered Tc 99m tilmanocept (n = 39). There were no Tc 99m tilmanocept related AEs. There were no deaths during the trial; no SAEs; and no AEs that led to discontinuation from the trial. In addition, radiation exposure was within regulatory and safety limits at the doses evaluated. Radiation exposure and pharmacokinetics do not appear to differ in subjects with RA and healthy control subjects.

1.2.5.3 NAV3-31 (IV)

This is an ongoing open-label, multi-center, single and repeat-dose study designed to evaluate the reliability and sensitivity of TUV assessments in HCs and subjects with active RA. One-hundred and five evaluable subjects will be enrolled. Tilmanocept is administered IV at a dose of 150 mcg tilmanocept radiolabeled with 10 mCi Tc 99m. Clinical safety conclusions for this study are still in progress.

2 STUDY OBJECTIVES

2.1 **Primary Objective(s)**

- To establish mean and variance of TUV_{joint} in HCs age-matched to RA population.
- To assess the feasibility of detecting Tc 99m tilmanocept anatomic localization using SPECT/CT imaging of hands and wrists in HCs and subjects with active RA.

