4.2.1 Inclusion Criteria

ALL SUBJECTS

- 1. The subject has provided written informed consent with HIPAA authorization before the initiation of any study-related procedures.
- 2. The subject has agreed to not engage in any diet, lifestyle, or medication changes until study completion.

HEALTHY CONTROL SUBJECTS

- 3. The subject is 30 years of age or greater at the time of consent.
- 4. The subject is deemed to be clinically free of any inflammatory disease(s), autoimmune disease(s), or arthropathies and has not experienced joint pain for at least 28 days prior to the consent date.

- 5. The subject is not currently on anti-inflammatory drugs (including NSAIDs) and has not taken any anti-inflammatories for at least 28 days prior to the consent date.
- 6. For all ongoing concomitant medications, the subject has maintained a stable dose for at least 28 days prior to the consent date.

CLINICALLY DIAGNOSED ACTIVE RA SUBJECTS

- 3. The subject is at least 18 years of age and was ≥ 18 years of age at the time of RA diagnosis.
- 4. The subject has moderate to severe RA as determined by the 2010 ACR/EULAR Classification Criteria (score of $\geq 6/10$).
- 5. The subject has a DAS28 of \geq 3.2 (includes the ESR test and VAS).
- 6. If the subject is receiving traditional DMARDs, they have been on therapy for ≥ 90 days and at a stable dose for ≥ 30 days prior to the imaging visit (Day 0).
- 7. If the subject is receiving bDMARD or JAK inhibitor therapy, they have been at a stable dose > 60 days prior to the imaging visit (Day 0).
- 8. If the subject is receiving NSAIDs or oral corticosteroids, the dose has been stable for ≥ 28 days prior to the imaging visit (Day 0). The corticosteroid dose must be ≤ 10 mg/day of prednisone or an equivalent steroid dose.

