9.4 Sample Size Justification

The study will enroll up to 135 evaluable subjects in Arms 1 and 2 allocated below, imaged at up to 8 study centers. Arm 1 will have N = 120 evaluable HC subjects, Arm 2 will have N = 15 (5 HCs and 10 RA) evaluable subjects. A subject is considered evaluable if he/she meets the criteria for the analysis population and has the data necessary for computing the primary endpoint.

The sample size for Arm 1 was determined to provide acceptable precision for the estimated 5 and 95 percentiles. These percentiles will be estimated with 95% nonparametric confidence intervals. Although the standard error formula for quantile estimators is known and quantile estimators obey a central limit theorem, relying on the asymptotic Normal distribution seems imprudent.

The sample will be stratified 3:1, females:males to reflect RA incidence in the United States [58, 59]. The sex-specific samples will be further stratified by age to reflect the Census estimated US population in 2019 (U.S. Census Bureau, 2020 [60]). The target sample sizes are given below.

Age Range	Male	Female	Total
30 to 39 years	8	23	31
40 to 49 years	7	21	28
50 to 59 years	8	22	30
60 to 69 years	7	21	28
70 years and older ^a	6	21	27
Total	36	108	144

^a An effort will be made to target enrollment in this group to include 2 men and 8 women 80 years old and over.

The existing data for HC subjects was used in a bootstrap procedure to evaluate the width of 95% confidence intervals for the 95 percentiles for various sample sizes. The sponsor has decided for its business purposes that knowing the percentile to within 0.05 of its true value is sufficient. A sample of size N = 144 HC results (this includes the subjects from Arm 1 of NAV3-31) in 95% confidence intervals with half-widths less than 0.05.

The sample size for Arm 2 was determined to be sufficient for the business purposes of the sponsor. The sample size for Arm 2 will be 5 HCs and 10 RA subjects.

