#### 1.3 Sample Size

The study will enroll up to 135 evaluable subjects in Arms 1 and 2 allocated below, imaged at up to 8 study centers.

Arm 1 will have up to N = 120 evaluable HC subjects, Arm 2 will have up to N = 15 evaluable subjects; 5 HCs and 10 RA subjects.

A subject is considered evaluable if he/she meets the criteria for the analysis population and has the data necessary for computing the primary endpoint(s) relevant to his/her study Arm.

The sample will be stratified 3:1, females to males ratio to reflect RA incidence in the United States. The sex-specific samples will be further stratified by age to reflect the Census estimated US population in 2019.

The target sample sizes are given below.

Age Range	Male	Female	Total
30 to 39 years	8	23	31
40 to 49 years	7	21	28
50 to 59 years	8	22	30
60 to 69 years	7	21	28
70 years and older	6	21	27
Total	36	108	144

An effort will be made to target enrollment in this group to include 2 men and 8 women 80 years old and over.

The existing data for HC subjects was used in a bootstrap procedure to evaluate the width of 95% confidence intervals for the 95 percentiles for various sample sizes. The sponsor has decided for its business purposes that knowing the percentile to within 0.05 of its true value is sufficient. A sample of size N = 144 HC results (this includes the subjects from Arm 1 of NAV3-31) in 95% confidence intervals with half-widths less than 0.05.

The sample size for Arm 2 was determined to be sufficient for the business purposes of the sponsor. The sample size for Arm 2 will be 5 HCs and 10 RA subjects.

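### The primary objective calls the healthy controls age-matched to RA, but the age quotas follow the US Census, so the limits describe a Census-aged group and may differ from those of an RA-aged group if TUV depends on age

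*Protocol*

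**What the plan says.** Protocol 2.1 states the first primary objective as "To establish mean and variance of TUV_{joint} in HCs age-matched to RA population". The phrase that matters here is "in HCs age-matched to RA population"; the protocol synopsis and SAP 1.0 say the same.

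Protocol 9.4 describes the sample. On sex: "The sample will be stratified 3:1, females:males to reflect RA incidence in the United States". On age: "The sex-specific samples will be further stratified by age to reflect the Census estimated US population in 2019". SAP 1.3 has the same age basis ("further stratified by age to reflect the Census estimated US population in 2019"). Protocol 8.1.1 says that HCs in either arm are categorised against these quotas so that the normative database has its intended distribution.

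Protocol 4.2.1 sets the HC age floor: "The subject is 30 years of age or greater at the time of consent". For RA subjects it is 18 years ("The subject is at least 18 years of age").

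Protocol 9.5.3.1 and SAP 4.2.1 estimate the 5th and 95th percentiles by quantile regression with an intercept only. SAP 4.1.2 and 4.2.2 examine TUV and its variance against age as secondary analyses. Neither section says what happens to the limits if age matters. Neither document gives an RA age distribution, a matching procedure or a weighting scheme.

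**The concern.** The objective claims a property that the design does not provide. The quotas match RA on sex and the general US population on age, and nothing in the primary analysis closes that gap. A report that the objective was met would describe a reference group that was not sampled.

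The limits are put to use. Protocol 9.5.3.4 calls a planar joint positive when its TUV exceeds the Arm 1 95th percentile. SAP 2.5 uses the normative mean and an upper limit of normal to identify inflamed joints and to build the global TUV. Protocol 3.1.1.3 looks ahead to reference values for people seen in clinic with symptoms. If TUV changes with age and RA patients are older than the quota sample, a pooled unweighted limit is not the 5% limit for healthy people of RA age.

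**Working it through.** **Quota table (protocol 9.4).** Men 8 + 7 + 8 + 7 + 6 = 36. Women 23 + 21 + 22 + 21 + 21 = 108. The total is 144 and 108/36 = 3.0, so the table and its sex ratio reproduce.

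**Flatness.** The band totals divided by 144 are 21.5%, 19.4%, 20.8%, 19.4% and 18.8%. Against five equal bands (28.8 each), chi-square = 0.375 on 4 df, p = 0.98. The youngest band, 30 to 39, is the largest.

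**Assumptions for the size of the effect.** None of these is in the documents.
- RA age mixes over the five bands: A 15/18/23/24/20%, B 10/15/25/28/22%, C 5/12/25/30/28%. All are older than the quotas.
- Band midpoints 35, 45, 55, 65 and 75 years.
- Within each band TUV is Normal with SD 1, and its mean rises by b = 0, 0.1, 0.2 or 0.3 SD per decade.

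**Mean.** The shift is b × (difference in mean age)/10. The quota mean age is (31×35 + 28×45 + 30×55 + 28×65 + 27×75)/144 = 7840/144 = 54.4 years. Mixes A, B and C give 56.6, 58.7 and 61.4. The largest shift is 0.3 × (61.4 − 54.44)/10 = 0.21 SD.

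**Limits.** With band weights w and band means m = b × (midpoint − 55)/10, the 95th percentile x solves Σ w Φ(x − m) = 0.95. The false-positive rate is Σ w [1 − Φ(x − m)], using the RA weights and the x found with the quota weights.

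| Mix | b | Mean shift (SD) | 95th percentile shift (SD) | Healthy joints above the Census-based limit |
|---|---|---|---|---|
| any | 0 | 0 | 0 | 5.0% |
| A | 0.1 | 0.02 | 0.02 | 5.2% |
| A | 0.3 | 0.07 | 0.05 | 5.5% |
| B | 0.1 | 0.04 | 0.04 | 5.4% |
| B | 0.3 | 0.13 | 0.09 | 6.0% |
| C | 0.1 | 0.07 | 0.06 | 5.7% |
| C | 0.3 | 0.21 | 0.16 | 6.7% |

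**SD.** The total SD is √(1 + variance of m). In the most extreme case it goes from 1.086 under the quotas to 1.058 under mix C, a change of 2.6%. This holds the within-band SD constant.

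**By age.** At the pooled limit, the healthy false-positive rate runs from 3.2% (30 to 39) to 7.3% (70 and older) at b = 0.1, and from 0.9% to 12.1% at b = 0.3.

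**Cost of standardising.** With quota shares q, the effective n is 144/Σ(w²/q): 144/1.035 = 139 for A, 144/1.123 = 128 for B and 144/1.267 = 114 for C.

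**Sampling error for scale.** At n = 144 the shortest exact order-statistic 95% interval for the 95th percentile uses ranks 131 to 142 (coverage 96.3%). Its mean half-width under Normality is about 0.39 SD.

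**The case against.** The endpoint, the quotas and the analysis agree with one another. Protocol 9.3 and SAP 4.1.1 define the limits in HC subjects without mentioning matching, so one phrase in the objective is out of step. Near-equal bands are also a sensible choice for studying age trends, and the SAP already plans age scatter plots, correlations and residual plots that would show dependence. All of this stands. It makes the point a correction of the stated reference population rather than a fault in the sampling, but it leaves the phrase uncorrected and the age analyses unconnected to the limits.

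The numerical effect may be nil, and under the assumptions above the shift in the 95th percentile is smaller than its sampling half-width. That also stands, although a larger sample would reduce sampling error and would not change the population sampled.

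A reader might take the 30 versus 18 age floors as proof of mismatch. They are not. The 18-year floor is an eligibility limit for 10 RA subjects in a feasibility arm and says nothing about the age distribution of RA. It shows only that an RA subject under 30 could be judged against limits with no healthy data at that age.

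**Conclusion.** The objective states age-matching to RA, and the design does not provide it. This follows from the text alone. The mean and the 5th and 95th percentiles will be those of a Census-aged group of 30 or older with an RA-like sex ratio.

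A reader might go further and infer that these values are wrong for an RA-aged group. The documents do not support that. It needs both an RA age mix unlike the quotas and a TUV that varies with age. The documents give no figure for either, and the SAP treats age dependence as an open question. The supported statement is that the values may differ if TUV depends on age. Under the assumed mixes and slopes the mean moves by 0 to 0.21 SD, the 95th percentile by 0 to 0.16 SD, and the healthy false-positive rate is 5.0% to 6.7%.

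Nor is there support for saying that the variance is materially misstated: under the same model the SD changes by at most 2.6%. The model does not cover a within-age SD that itself changes with age, which the SAP also leaves open.

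**What to change.** Reword the objective in the protocol synopsis, protocol 2.1 and SAP 1.0 to: HCs aged 30 years or older with the RA sex ratio and the US Census age distribution. State beside the limits that they are not established below age 30. This costs only a wording change.

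Add one supportive analysis to SAP 4.2, triggered if the planned age analyses show dependence. Report the mean and the 5th and 95th percentiles standardised to a cited RA age distribution, or put age in the quantile regression, and show the result beside the unweighted limits. The unweighted limits stay primary. Standardising needs an age distribution from outside these documents, and it costs some precision: an effective n of about 114 to 139 of 144 under the assumed mixes. The half-width target of 0.05 was set for the unweighted sample, so the standardised estimate should not be presented as meeting it without a check. No new subjects or procedures are needed.
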